38 1) Change in clinical status as captured by 7-point ordinal scale score (being utilized in Gilead Sciences
39 remdesivir trial^{19, 20}) at time of plasma infusion (day 0) compared to day 7:

40

- 44 1. Death
- 45 2. Hospitalized, requiring mechanical ventilation or ECMO

- 1 3. Hospitalized, requiring non-invasive ventilation or high flow oxygen
- 2 4. Hospitalized, requiring supplemental oxygen
- 3 5. Hospitalized, not requiring supplemental oxygen--requiring ongoing medical care
- 4 (COVID-19 related or otherwise)
- 5 6. Hospitalized, not requiring supplemental oxygen-not requiring ongoing medical care
- 6 (COVID-19 related or otherwise).
- 7 7. Not Hospitalized

8 2) Adverse events related to plasma infusion (within 6 hours of infusion) to include²³:

- 9 a) Transfusion-related events
 - 10 i. Transfusion Associated Circulatory Overload
 - 11 ii. Transfusion-Related Lung Injury
 - 12 iii. Allergic Reaction/Anaphylaxis
 - 13 iv. Transmission of transfusion transmitted diseases
 - 14 v. Febrile Transfusion Non-hemolytic Transfusion Reaction

15 Secondary Endpoints:

- 16 3) Change in 7-point ordinal scale score (being utilized in Gilead Sciences remdesivir trial) from time
- 17 of plasma infusion (day 0-prior to first infusion) to days 14, 21, and 28^{19,20}.
- 18 4) SOFA score at days 0, 7, 14, 21, 28²¹
- 19 5) Time to discontinuation of supplemental oxygen
- 20 6) Duration of hospitalization
- 21 7) Time to liberation from mechanical ventilation (for patients on a ventilator)
- 22 8) Need for mechanical ventilation (For those not on the ventilator)
- 23 9) All-cause Mortality [at 28 days]

24 ○

| Organ System, Measurement | SOFA Score | | | | |
|--|------------|-------------------|--|--|---|
| | 0 | 1 | 2 | 3 | 4 |
| Respiration PaO ₂ /FiO ₂ , mmHg | Normal | <400 | <300 | <200 (with respiratory support) | <100 (with respiratory support) |
| Coagulation Platelets x10 ³ /mm ³ | Normal | <150 | <100 | <50 | <20 |
| Liver Bilirubin, mg/dL (μmol/l) | Normal | 1.2-1.9 (20-32) | 2.0-5.9 (33-101) | 6.0-11.9 (102-204) | >12.0 (<204) |
| Cardiovascular Hypotension | Normal | MAP<70 mmHg | Dopamine ≤5 or dobutamine (any dose)** | Dopamine >5 or epinephrine ≤0.1 or norepinephrine ≤0.1 | Dopamine >15 or epinephrine >0.1 or norepinephrine >0.1 |
| Central Nervous System Glasgow Coma Score | Normal | 13-14 | 10-12 | 6-9 | <6 |

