25 appropriate. Treating physician will notify the study doctor and staff if there is an adverse reaction.

26 Possible anticipated infusion related reactions could include:

27 1) Transfusion Associated Circulatory Overload – dose of intravenous furosemide may be
28 considered
29 2) Transfusion-Related Lung Injury- supportive care as directed by treating physician
30 3) Allergic Reaction/Anaphylaxis – additional dose of diphenhydramine, dose of intravenous or oral
31 corticosteroids or intramuscular epinephrine could be considered
32 4) Transmission of transfusion transmitted diseases – supportive care or targeted treatment if
33 infection identified
34 5) Febrile Transfusion Non-hemolytic Transfusion Reaction – supportive care

35 These adverse events, if present, will be recorded by clinical research team.

36

37 **Post-Treatment Blood Draws:**

38 Optional blood draws (up to four tubes) may be drawn on days 7, 14, 21, and 28 (+/2 days) following each
39 dose of convalescent plasma where feasible for Biobanking.

40 If patient is discharged prior to 7 days post-dosing, then follow-up phone call or email assessments
41 will be made by study staff at 7 days, 14 days, 21, and 28 days (+/2 days) following the original dose.

1
2 **Script for Phone Call(s) or Email(s) to Recipients (if applicable):**

3 1) Are you in a home environment (your home or family member's home)?
4 2) If not, are you in a nursing or rehabilitation facility?
5 3) Are you using oxygen?
6 4) Have you required an urgent care or emergency room visit for any reason since your
7 discharge?
8 5) Have you required re-hospitalization for any reason since your discharge?

9
10 **Trial Methods**

11 Convalescent plasma will be made available to patients hospitalized in the Inova Heath System.

12
13 Patient outcome monitoring and reporting will include indicators of safety and efficacy. Case Report
14 Forms will be used to capture essential data.

15
16 **Statistical Plan**

17 Study parameters (e.g., clinical status scale, death, hospitalization, etc.) will be described using traditional
18 descriptive statistics (median [IQR], frequency and percent). Data will be assessed for 'missingness' with
19 parameters exceeding 10% missing explored for imputation (e.g., multiple imputation, last value carried
20 forward, etc.). Departures from normality will be assessed via Shapiro-Wilkes test with data

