21 transformations explored as needed. All analyses will be conducted using SAS (version 9.4, Cary, NC)
22 with p<0.05, two-tailed considered statistically significant.

23
24 Primary efficacy endpoints:

25 1. Gilead 7-point scale – For each time point (day 0 vs. 7), summary clinical status scores will be
26 calculated. Changes in scores will be subsequently assessed via a generalized linear mixed model
27 with clinical status assessed at day 0 vs. 7. A statistically significant increase of ± 2 points in β
28 from day 0 to day 7 will be considered as evidence of efficacy. A mixed model allows for
29 examination and inclusion of the variance-covariance matrix into the model as a result of expected
30 within-subject serial correlation as a result of repeated assessments over time.
31 2. Plasma transfusion related adverse events will be scored as 1+ vs. 0 and will be assessed via Chi-
32 Square test with a hypothesized distribution of expected AE (using the higher incidence estimate):
33 i. Transfusion Associated Circulatory Overload: 1:1,566 to 1:68 plasma units
34 transfused
35 ii. Transfusion-Related Lung Injury: 1:1,200 to 1:190,000
36 iii. Allergic Reaction/Anaphylaxis: 1-3%
37 iv. Febrile Transfusion Non-hemolytic Transfusion Reaction: 0.1-1%

38
39 Secondary endpoints:

40 1. Change in 7-point ordinal scale score and SOFA score over time will be assessed via individual
41 growth models (IGM). Times will be day0, 14, 21, and 28
42 2. Mortality will be assessed via Chi-Square test with a hypothesized current mortality rate of 1-5%
43 (age adjusted).
44 3. Need for mechanical ventilation for those not ventilator at time of plasma infusion will be
45 assessed via Chi-Square test with a currently available published estimates.

1 4. Time to discontinuation of supplemental oxygen, time to liberation from mechanical ventilation,
2 duration of hospitalization will be summarized as median (IQR) or rates and compared to currently
3 available published estimates.
4
5

6 **ADVERSE EVENTS AND TOXICITY MANAGEMENT**

7 **Definitions of Adverse Events and Serious Adverse Events**

9 **Adverse Events (AE)**

10 An AE is any untoward medical occurrence in a clinical study subject administered an investigational
11 product, which does not necessarily have a causal relationship with the treatment. An AE can therefore be
12 any unfavorable and/or unintended sign, symptom, or disease temporally associated with the use of an

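### Secondary item 4 gives no rule for deaths or unreached events in three time summaries, so a plain median can look too short

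*Combined protocol and SAP*

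**What the plan says.** The Statistical Plan (Secondary endpoints, item 4) covers three time measures in one sentence, which ends: "duration of hospitalization will be summarized as median (IQR) or rates and compared to currently" published estimates. No source is named for those estimates, and the study has no control arm.

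The endpoint list in the protocol (Secondary Endpoints, items 5-7) gives the three measures by name only. One entry reads in full "Time to discontinuation of supplemental oxygen", with no at-risk group. Ventilator liberation is limited to patients on a ventilator, without saying when. The opposite transition is better specified in the Statistical Plan, item 3: "Need for mechanical ventilation for those not ventilator at time of plasma infusion will be" tested against published estimates. None of the three time measures has a stated time origin or horizon.

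The general text of the Statistical Plan adds "descriptive statistics (median [IQR], frequency and percent). Data will be assessed for 'missingness' with" "parameters exceeding 10% missing explored for imputation (e.g., multiple imputation, last value carried" forward and similar methods. Censoring, cumulative incidence and competing risks are not mentioned anywhere.

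Two other statements matter here. On mortality, item 2 says "Mortality will be assessed via Chi-Square test with a hypothesized current mortality rate of 1-5" per cent, age adjusted. The ordinal scale, which has death as its lowest level, is also analysed from the time "of plasma infusion (day 0-prior to first infusion) to days 14, 21, and 28".

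**The concern.** Recipients have severe or life-threatening disease, so some will foreseeably die on oxygen or on a ventilator. Such a patient has no time to discontinuation or liberation. A plain median over recorded times leaves that patient out, and it does the same for anyone who has not reached the event when observation ends. Hospital stay has a second route to the same problem: an in-hospital death has an end date, and using it counts death like discharge. Either way the median can be shorter than what all patients at risk experienced.

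The plan's only use of these medians is to set them beside published times. That comparison can be read only if both sides share a time origin and a rule for deaths. Offering a median or rates does not settle this, because a rate without a denominator and horizon has the same gap.

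**Working it through.** The documents give no median, event count or power figure for these endpoints, so there is nothing to reproduce. The calculation below only shows direction and size.

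**Direction.** Let C(t) be the share of all at-risk patients who have reached the event by time t. The event-only median is the time when C(t) reaches half its final value. The all-at-risk median is the time when C(t) reaches 0.5. Half the final value cannot exceed 0.5, so the event-only median can never be the later of the two.

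**Inputs.** From the plan: mortality 1-5% (Statistical Plan, Secondary endpoints, item 2). Assumed: a recovery median of 10 days; p, the share dying before the event, equal to mortality; 30% mortality as a stress value; a day-28 cutoff in step 2.
- Model A: constant hazards. Event hazard l = ln2/10 = 0.0693; total hazard T = l/(1-p).
- Model B: log-normal recovery times, median 10, sigma 0.5, unaffected by mortality.

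**Step 1: death alone, complete follow-up.**
- Model A: event-only median = 10(1-p); all-at-risk median = -ln(1-0.5/(1-p))/T.
- Model B: event-only median = 10; all-at-risk median = 10·exp(0.5·z(0.5/(1-p))), with z the normal quantile.

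| p | A: event-only / all at risk | A: gap | B: event-only / all at risk | B: gap |
|---|---|---|---|---|
| 1% | 9.90 / 10.05 | 0.15 | 10.00 / 10.06 | 0.06 |
| 5% | 9.50 / 10.24 | 0.74 | 10.00 / 10.34 | 0.34 |
| 30% | 7.00 / 12.65 | 5.65 | 10.00 / 13.27 | 3.27 |

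**Step 2: add an assumed cutoff at day 28.**
- Model A: event share = (1-p)(1-exp(-28T)); event-only median = -ln(1-0.5(1-exp(-28T)))/T.
- Model B: F(28) = 0.980; event share = (1-p)F(28); event-only median = 10·exp(0.5·z(0.5·F(28))) = 9.88 for every p.

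| p | A: event-only / all at risk | A: gap | A: no event | B: gap | B: no event |
|---|---|---|---|---|---|
| 0 | 8.06 / 10.00 | 1.94 | 14.4% | 0.12 | 2.0% |
| 1% | 8.02 / 10.05 | 2.03 | 14.9% | 0.19 | 3.0% |
| 5% | 7.83 / 10.24 | 2.41 | 17.3% | 0.46 | 6.9% |
| 30% | 6.39 / 12.65 | 6.26 | 34.4% | 3.39 | 31.4% |

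In Model A, 1.94 of the 2.41 days at 5% mortality are already there with no deaths, so they come from the cutoff. With a 14-day recovery median the gaps at 1-5% mortality are 4.61-5.05 days (A) and 0.80-1.18 days (B).

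**Step 3: hospital stay with death as the end of stay (Model B).** Solve (1-p)F_discharge(t) + p·F_death(t) = 0.5, with sigma 0.5 for both and an assumed median day of death of 5, 10 or 20.

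| p | Stay ending at death or discharge (death day 5 / 10 / 20) | Discharge alive, all at risk |
|---|---|---|
| 1% | 9.95 / 10.00 / 10.05 | 10.06 |
| 5% | 9.73 / 10.00 / 10.27 | 10.34 |
| 30% | 8.28 / 10.00 / 12.08 | 13.27 |

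At 5% mortality the largest gap is 10.34 - 9.73 = 0.61 days.

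**Cross-check.** Constant hazards can instead be set from day-28 shares. With 1% dead and 5% alive without the event, the event-only median is 6.0 against 6.6 days; with 5% and 30%, it is 10.0 against 18.0. The direction is the same. The size follows the assumed unresolved share.

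**The case against.** The plan does not say that the median is restricted to observed events, and a rate over all at-risk recipients would avoid the problem. That is correct, and it is why the point says the summary can look short, not that it will.

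The larger figures rest on assumptions. Day 28 is stated for mortality, the ordinal scale, SOFA and the contacts after early discharge, but nothing ends observation of inpatients on that day. Ventilator liberation and discharge are seen in hospital, so unresolved patients could be few for two of the three measures. This stands and limits the size that can be claimed.

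The study also reports 28-day mortality and an ordinal scale that ranks death worst. Both help a reader, but neither is linked to these summaries, and the top category, "7. Not Hospitalized", does not show oxygen use after discharge.

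A reader might infer three stronger things that the documents do not support:
- **That recovery times would be imputed for patients who died.** The missing-data text says only that imputation will be explored, and nothing in it classes death as missing.
- **That a fixed number of patients would drop out of the hospital-stay median.** At 5% mortality and 150-200 recipients, the day-28 models give 0.173 × 150-200 = 26-35 (A) or 0.069 × 150-200 = 10-14 (B). If observation runs to discharge and death ends the stay, none is left out.
- **That the comparison is biased in favour of plasma.** The published figures may use the same convention, in which case part of the gap cancels.

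**Conclusion.** The point holds as a minor-to-moderate weakness in secondary summaries. Item 4 names a plain median or rates for measures on which death prevents the event, and no section says how deaths or unreached events count. Against the all-at-risk median, an event-only median can only err towards a shorter time.

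At the plan's 1-5% mortality, death alone moves the median by about 0.1-0.7 days (0.06-0.74 across the two models), given an assumed 10-day recovery median. Gaps of two days or more need mortality well above 5%, or many patients unresolved at an assumed day-28 cutoff with long-tailed or slower recovery. The net direction against the unnamed published figures is unknown. The primary endpoints are not affected.

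**What to change.** Rewrite item 4 as follows.
- **Origin and at-risk sets.** Measure from first infusion (day 0): patients on oxygen at day 0, patients on a ventilator at day 0, and all recipients for discharge alive.
- **Estimator.** Replace the plain median with the cumulative incidence of the event to day 28, with death as a competing event, all at-risk patients in the denominator and n/N shown. Give a median only if incidence reaches 50%.
- **Oxygen after discharge.** Where the stop date is not known, report the proportion alive and off oxygen at days 7, 14, 21 and 28, with unknown status shown.
- **Deaths.** State that event times are not imputed for patients who die.
- **Published figures.** Treat them as context unless they use the same time origin and the same rule for deaths.

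The cost is slightly more analysis work with a standard estimator, estimates that look less favourable, and fewer published figures that can be compared directly.

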4 will be performed to permit retrospective determination of the characteristics of an effective product and
5 dosage regimen, and the characteristics of patients most likely to benefit¹⁸.

6 Data and blood specimen will be banked for future use pursuant to the IRB Approved Inova COVID-19
7 Biobanking Protocol. We will follow the guidelines and procedures for specimen storage and access as
8 described in the IRB approved Inova COVID-19 Biobanking Protocol.

9 Specimens will be stored at the Office of Research at Inova Biobank with standard certifications in place.

10

1 **PLASMA RECIPIENTS:**

2 **Inclusion Criteria for Recipients of COVID-19 Convalescent Plasma:**

3 Patients in the Inova Health System with confirmed COVID-19 by PCR testing

4 Age \geq 13 years

5 Currently hospitalized with COVID-19 infection with severe or life-threatening clinical syndrome²² as
6 follows:

7 Severe COVID-19: (three or more of the following)

8

- 10 • Dyspnea
- 11 • Respiratory rate \geq 30/min
- 12 • Blood oxygen saturation (SpO₂) \leq 94% on room air
- 13 • Partial pressure of arterial oxygen to fraction of inspired oxygen (P:F) ratio $<$ 300
- 14 • Pulmonary infiltrates $>$ 50% of lung parenchyma within 24 to 48 hours

15 Life-threatening disease is defined as: (one of the following)

- 16 • Respiratory failure
- 17 • Septic shock, and/or
- 18 • Multiple organ dysfunction or failure

19 Patient must provide informed consent or have health care power of attorney/next of kin provide consent
20 if he/she cannot.

21 **Exclusion Criteria:**

22 Contraindication to receive plasma as deemed by the treating physician

23 Severe hypercoagulable state (documented in medical chart or by treating physician assessment)

24 Absolute IgA deficiency

25 Prior history of Transfusion Related Acute Lung Injury (TRALI)

26 Inability to tolerate plasma volume due to severe systolic or diastolic heart failure despite slower infusion
27 and diuretic administration

28 Positive pregnancy test (HCG)

29 **Recipient Screening Labs**

30 Blood Type

31 Total immunoglobulin (Ig) levels: IgG, IgA, IgM

32 Coagulation tests to include PT/INR and PTT

33 Complete blood count and differential

34 **Pre-Treatment Testing:**

35 Optional Blood draw for Inova COVID-19 Biobank (up to four tubes each) prior to each dose of plasma

36 **Target Recipient Recruitment:** 150-200 individuals

37 **Primary Endpoints:**

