| Renal Creatinine, mg/dL (μmol/l) or Urine output | Normal | 1.2-1.9 (110-170) | 2.0-3.4 (171-299) | 3.5-4.9 (300-440) or <500 mL/day | >5.0 (>440) or <200 mL/day |

26 * Source: [Vincent et al., 1996](#).

- 27 10) All other adverse and serious adverse events will be recorded as well (see adverse events section to follow).
- 28 11) Change in standard of care inflammatory markers (ferritin, LDH, CRP, D-dimer) where available
- 29 from day 0 to days 7, 14, 21, 28.

1 Exploratory Endpoints:

2 12) Association between antibody levels and donor characteristics/clinical course
3 13) Association between clinical response in recipients and antibody levels in the donors

4

5 **Dosing:**

6 • One dose of 200-300mL (standard collection bag volume) of convalescent plasma will be infused
7 over approximately one hour intravenously with standard vital sign monitoring per unit protocol
8 and standard of care for plasma infusion.

9 • Up to two additional doses of 200 mL of convalescent plasma may be administered within 14 days of initial
10 dose at 1-7 day intervals according to disease severity and tolerance of the infusions. Where possible,
11 plasma from distinct donors will be used for additional doses.

12 • To reduce probability of allergic reaction, pre-medication with diphenhydramine 25mg orally or
13 intravenously will be given within 2 hours before each dose of plasma, unless there is a
14 contraindication noted by treating physician.

15 • Slower infusion time of two hours with optional dose of 20mg intravenous furosemide after first
16 hour can be considered for patients at risk for transfusion-associated circulatory overload

17 • Infusion can be slowed for patient comfort at any time.

18 **Safety:** Patients will be monitored closely during plasma infusion per Inova nursing policy titled
19 “Transfusion/Infusion of Blood Components” Version 01.01. Patients will remain in the hospital for a minimum
20 of 24 hours post-infusion with vital signs performed per standard of care with frequency based on the
21 treating hospital unit. Patients will be discharged from hospital according to standard of care any time
22 after completion of 24 hour observation period post-infusion dosing.

23 If oxygenation worsens post-infusion, treating physician will perform assessment as to the presence of a
24 transfusion related reaction, increase oxygen delivery, and obtain portable chest film if deemed clinically

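### Three recovery times are compared with unnamed published estimates without a stated time origin, although recipients enter part-way through their stay, so the comparison can differ from the benchmark with no plasma effect.

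*Combined protocol and SAP*

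**What the plan says.** The endpoint list names "Time to discontinuation of supplemental oxygen", "Duration of hospitalization" and "Time to liberation from mechanical ventilation (for patients on a ventilator") as secondary endpoints 5, 6 and 7. None of these entries says when the clock starts.

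The Statistical Plan handles all three in secondary endpoint 4. It lists the oxygen and ventilator times and then says that "duration of hospitalization will be summarized as median (IQR) or rates and compared to currently" "available published estimates". No source, value or time origin is given for those estimates, and no test is named.

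Elsewhere the protocol does fix an origin. The ordinal scale is measured from the time "of plasma infusion (day 0-prior to first infusion) to days 14, 21, and 28". SOFA and the inflammatory markers use the same day numbering, and calls after early discharge are timed from the first dose. The three time outcomes are not tied to that day 0.

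The recipient inclusion criteria require a patient to be "Currently hospitalized with COVID-19 infection with severe or life-threatening clinical syndrome". They set no limit on days since admission, oxygen start or intubation. Consent, screening labs including blood type, and ABO-compatible plasma all come before infusion. After infusion the recipient stays for a minimum "of 24 hours post-infusion with vital signs performed per standard of care with frequency based on the" treating unit. There is no concurrent control group.

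**The concern.** A patient discharged or dead before infusion cannot become a recipient. Everyone in the recipient group has therefore been in hospital up to the infusion and, for the oxygen and ventilator outcomes, is still on that support at infusion. A published series that counts every patient from admission or intubation has no such condition.

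The choice of clock then matters. Duration of hospitalization in its ordinary sense runs from admission, so it includes time that every recipient was bound to complete before treatment. The other two outcomes could run from infusion, oxygen start or intubation. With the origin open on both sides, the difference from the benchmark depends partly on the analyst's choice and on how late plasma was given.

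The study is single-arm, so this comparison is its only between-group evidence on these three outcomes, and they bear directly on the hypothesis of faster recovery. The problem is separate from how deaths and unresolved stays are counted: it remains with complete follow-up and no deaths.

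**Working it through.** The plan gives no benchmark value, delay or effect size for these outcomes, so there is no figure of its own to reproduce. The check asks what each clock would show if plasma did nothing.

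**Inputs.** From the documents: entry while in hospital, no time window, no stated origin, comparison with published figures. Assumed: the benchmark counts from admission with a median stay of 10 days; stays follow a Weibull distribution with shape k; infusion is on day e = 5; recipients are a random sample of patients still in hospital on that day.

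**Formula.** S(t) = exp(−(t/L)^k), with L = 10/(ln 2)^(1/k) so that the median is 10. Given a stay beyond e, the median from admission solves S(t) = S(e)/2:

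t = L·((e/L)^k + ln 2)^(1/k) = 10·((e/10)^k + 1)^(1/k).

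The median from infusion is t − e.

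**Numbers for e = 5.**

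- k = 1 (constant discharge rate): t = 10 × (0.5 + 1) = 15.0 days from admission; 15.0 − 5 = 10.0 from infusion.
- k = 1.5 (rising rate): t = 10 × (0.5^1.5 + 1)^(1/1.5) = 12.2; 7.2 from infusion.
- k = 2 (rising faster): t = 10 × (0.25 + 1)^(1/2) = 11.2; 6.2 from infusion.
- k = 0.75 (falling rate): t = 10 × (0.5^0.75 + 1)^(1/0.75) = 18.6; 13.6 from infusion.

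Against the benchmark of 10, shapes 1, 1.5 and 2 look 50%, 22% and 12% longer from admission. From infusion they look equal, 28% shorter and 38% shorter. At shape 0.75 the from-infusion median looks 36% longer. For e = 10 and k = 2, t = 10 × √2 = 14.1 from admission and 4.1 from infusion.

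**Cross-check by simulation** (2,000,000 stays per scenario, no plasma effect, same 10-day benchmark; exponential, Weibull 1.5 and lognormal with log-SD 0.7, in that order):

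- Infusion on day 2: 12.0, 10.6, 10.1 days from admission; 10.0, 8.6, 8.1 from infusion.
- Infusion on day 4: 14.0, 11.6, 10.9 from admission; 10.0, 7.6, 6.9 from infusion.
- Infusion uniform over days 0–7: 13.3, 11.4, 10.9 from admission; 10.0, 8.1, 7.6 from infusion.
- Infusion on day 0 (recipients and benchmark share the origin): 10.0 on both clocks for all three.

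The from-admission median exceeds 10 in every case with a delay. The from-infusion median has no fixed direction.

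**The case against.** Context partly supplies an origin. Infusion is day 0 for the scores and the start of the follow-up calls, so it is a reasonable default for the two time-to-event outcomes. That is an inference, and it does not carry over to duration of hospitalization, which ordinarily runs from admission.

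The plan does not rule out a published series of severe inpatients counted from start of treatment, which would remove much of the problem. That is correct, but nothing in the plan requires one.

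A reader might infer that both clocks are biased and that counting from infusion always flatters plasma. The documents do not support this. With a constant discharge rate the from-infusion median is unchanged, and with a falling rate it is longer than the benchmark. Nothing in the protocol says which pattern holds.

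A reader might also infer that patients can enter at literally any point of the stay. Entry requires three or more severe criteria or one life-threatening criterion; what is missing is a time limit once those are met.

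Finally, these are secondary outcomes, no success rule rests on them, and case-mix differences from published cohorts would remain even with aligned clocks. All of that stands. It limits the weight of the point but does not remove it.

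**Conclusion.** The point holds in this form: the origin is missing for all three times, and entry is delayed and conditional on still being in hospital or on support. With no plasma effect, times counted from admission, oxygen start or intubation look longer than in a series that starts there. Times counted from infusion may differ from that series in either direction, or not at all.

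For infusion on day 5 and shapes 0.75 to 2, the illustrated shift runs from 12% to 86% longer from admission, and from 38% shorter to 36% longer from infusion. These sizes rest wholly on the assumed 10-day benchmark, its admission origin, the infusion day and the stay distribution. They show that the effect can be large, not how large it will be here.

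It would be going too far to speak of a false-positive rate for this plan. A rate can be calculated for an assumed test, but secondary endpoint 4 specifies none. The harm is a misleading descriptive comparison. The change should be made, but it does not affect the primary analysis.

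**What to change.** In secondary endpoint 4, set time zero at the first infusion for all three outcomes, and record the chart dates of admission, oxygen start and intubation for each recipient. Name the published source, and compare only if it has the same origin and a similar severity condition. If no such series exists, report the median (IQR) descriptively, with no comparison and no inference about efficacy.

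A delayed-entry (left-truncated) estimate, in which each recipient joins the risk set on the day of infusion, may be added as a sensitivity analysis against an admission- or intubation-based figure. It should carry two warnings. Its early risk sets are small. It also assumes that infusion timing is unrelated to prognosis, which is doubtful when entry depends on severity. In one null simulation, half the patients recovered fast (median 6 days) and half slowly (median 16 days), Weibull shape 1.5, with slow patients infused at 2–3 times the rate. The true median was 9.3 days and the delayed-entry median 10.5–11.0, a spurious lengthening of about 13–19%. For that reason it should not be the main comparison.

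The cost is a few sentences in the Statistical Plan and three chart dates per recipient; enrolment and treatment do not change. The downside is that the comparison may have to be dropped if no matched series is found.
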